6.6 Safety Assessment Method and Timing

At each study assessment conducted either in the clinic or by telephone, the Investigator or designee will ask the subject non-leading questions to obtain reports of any change in medical condition or diagnosis consistent with the AEs of interest or SAEs related to ADVM-043 (Section 6.2 and Section 6.3).

A plan for scheduled visits with an HCP to elicit and record new findings for each study subject, including history, physical examination, or laboratory testing will be included in the study manual in accordance with the FDA guidance on the design of long term follow-up observational studies for the collection of data on delayed adverse events following administration of gene therapy products (FDA Draft Guidance for Industry 2018).

Information to be collected includes event term per CTCAE Version 5.0 (National Cancer Institute 2017); date of onset; Investigator assessment of seriousness, severity, and relationship to ADVM-043; date of resolution of the event; any required concomitant medication or treatment; evaluations for malignancies and results such as biopsy results; and outcome.

6.7 Adverse Event Reporting

The Investigator or designee is to be responsible for collecting all events that meet the definition of AEs of interest (Section 6.2). AEs of interest should be recorded on the CRF by the Investigator or designee

6.8 Serious Adverse Event Reporting

SAEs related to ADVM-043 should be recorded on the CRF by the Investigator or designee (Section 6.3). The Investigator must report a related SAE to the Sponsor within 24 hours of awareness of the event to meet regulatory and patient safety obligations. For additional details on reporting of safety reports please refer to the Investigator Study Manual.

6.9 Follow-up of Subjects Reporting an Adverse Event

SAEs related to ADVM-043 and AEs of interest should be followed until satisfactory resolution or until the Investigator deems the event to be stable.

6.10 Request for Autopsy in the Event of a Subject Death

In the event of a subject death while participating in the study, the Investigator should request a full autopsy to determine the precise cause of death. If possible, samples of tissues obtained at autopsy should be evaluated for the presence of the AAV genome.

7.0 ASSESSMENT OF EFFICACY

Not applicable

8.0 STATISTICAL PLAN

Descriptive and exploratory analyses are to be performed on all data to gain insight into the safety of ADVM-043. Adverse event data are to be analyzed overall, by dose level administered, and by study. Refer to the Statistical Analysis Plan.

9.0 ETHICAL CONSIDERATIONS

9.1 Independent Ethics Committee / Institutional Biosafety Committee

Federal regulations and the ICH guidelines require that approval be obtained for each clinical site from an independent ethics committee / institutional biosafety committee (IEC / IBC) before participation of human subjects in research studies. Before study onset, the protocol, informed consent form, and any other written information regarding this study to be provided to the subject or the subject's legal guardian must be approved by the IEC / IBC, and written confirmation of such approval must be received by the site. Documentation of all approvals and of the IEC / IBC compliance with ICH Guideline for Good Clinical Practice (E6) will be maintained by the site and will be available for review by the Sponsor or its designees.

All approvals should be signed by the IEC / IBC chair or designee and must identify the IEC / IBC by name and address, the clinical protocol by title or protocol number or both, and the date approval or favorable opinion was granted.

9.2 Ethical Conduct of the Study

The study is to be performed in accordance with the ethical principles that have their origin in the Declaration of Helsinki and Council of International Organizations of Medical Sciences (CIOMS) Ethical Guidelines, and in accordance with the International Council for Harmonization (ICH) Harmonized Tripartite Guideline E6: Good Clinical Practice; 21 CFR; and applicable laws and regulations.

This study will be conducted in compliance with the protocol approved by the IEC / IBC, and according to GCP standards. No deviation from the protocol will be implemented without the prior review and approval of the Sponsor and the IEC, except where it may be necessary to eliminate an immediate hazard to a subject enrolled in this study. In such case, the deviation will be reported to the IEC as soon as possible.

9.3 Subject Information and Consent

The study-specific informed consent form (ICF) and the informed consent process must comply with the Declaration of Helsinki, US Title 21 Code of Federal Regulations (CFR) Part 50, HIPAA (if applicable), and local laws. The Investigator will draft the informed consent form, assent, and HIPAA authorization (if applicable) and submit the draft for review and comment by the Sponsor, and Investigator will submit the mutually agreed upon ICF, ascent, and HIPPA authorization (if applicable) to the IEC/IBC for approval.

The Investigator or designee (designee listed on the Delegation of Responsibilities log) must explain in terms understandable by the subject the content of the informed consent form including the purpose and nature of the protocol, procedures, anticipated benefit, potential risks, possible AEs, and any discomfort that participation in the protocol may entail. This process must be documented in the subject's source record. Each subject or legally acceptable representative must be allowed to read the ICF under conditions where there is adequate time to consider the risks and benefits associated with participation.

Before any study-specific procedure or test is performed, the Investigator must be certain that the subject or legally acceptable representative understands the implications of participation in the study. The subject or legally acceptable representative and the Investigator must sign and date the ICF before such subject is entered into the study. The Investigator is to retain the signed ICF and give a copy of the signed form to the subject or legally acceptable representative. The process of obtaining informed consent is to be documented in the subject's records.

The Investigator or designee shall maintain a log of all subjects who have signed ICF, or whose legally acceptable representative has signed the ICF; and indicate whether the subject was enrolled or the reason for non-enrollment.

If the ICF is revised during the study, any institution-specific modifications proposed by the site should be reviewed and approved by the Sponsor or designee before IEC submission.

10.0 INVESTIGATOR'S RESPONSIBILITIES

A complete list of Investigator responsibilities is outlined in the Clinical Trial Agreement and, for US Investigators, the Statement of Investigator Form FDA 1572, signed by the Investigator before commencement of the study. In summary, the Investigator will conduct the study according to the current protocol, the Statement of Investigator, the general investigational plan, and applicable laws and regulations; will read and understand the Investigator's Brochure; will obtain IEC / IBC approval to conduct the study; will obtain informed consent from each study participant prior to their participation in the study; will maintain and supply to the Sponsor or designee, auditors, and regulatory agencies adequate and accurate records of study activity and drug accountability for study-related monitoring, audits, IEC / IBC reviews and regulatory inspections; will report SAEs to the Sponsor or designee and IEC / IBC according to the specifics outlined in this protocol, which reports shall include an assessment of whether there is a reasonable possibility that the study drug caused the AE; will personally conduct or supervise the study; and will ensure that colleagues participating in the study are informed about their obligations in meeting the above commitments.

11.0 SPONSOR RESPONSIBILITIES

A complete list of the Sponsor responsibilities is outlined in the Clinical Trial Agreement and in the laws and regulations of the country in which the research is conducted. In summary, the Sponsor will select qualified Investigators, provide them with the information they need to properly conduct the study, ensure adequate monitoring of the study, ensure that each Investigator conducts the study in accordance with the general investigational plan and protocol, and promptly inform Investigators and health and regulatory agencies as appropriate of significant new adverse effects or risks with respect to the drug.

11.1 Modification of the Protocol

Any changes in this research activity, except those necessary to remove an apparent, immediate hazard to a subject, must be reviewed and approved by the Sponsor prior to implementation. Protocol Amendments must be approved by the IEC / IBC before any subject can be enrolled into an amended protocol.

11.2 Protocol Deviations

A protocol deviation is any change, divergence, or departure from the procedures and processes as specified in the protocol. A significant protocol deviation occurs when there is nonadherence to the protocol that might significantly (a) impact the completeness, reliability, and / or accuracy of the study data, or (b) affect a subject's rights, safety, or well-being. The Investigator or designee must document and explain any protocol deviation in the subject's source documentation. Any significant protocol deviation will be investigated and reported by the Sponsor and may lead to the subject being withdrawn from the study, termination of the Investigator's participation in the study, and / or other actions.

The Sponsor will be notified of known significant protocol deviations by the Investigator. Protocol deviations found throughout the course of monitoring visits are to be documented by the clinical monitor. The IEC / IBC should be notified of all protocol deviations in a timely manner by the Investigator.

11.3 Confidentiality

Investigators must comply with all applicable privacy laws and regulations (e.g., HIPAA). Information on maintaining subject confidentiality in accordance with individual local and national subject privacy regulations must be provided to each subject as part of the informed consent process, either as part of the ICF or as a separate signed document. In the United States, a site-specific HIPAA-compliant authorization form may be used. The Investigator or designee must explain to each subject that for the evaluation of study results and potential marketing approval, the subject's protected health information obtained during the study may be disclosed to the Sponsor and its designees, regulatory agencies, and the IEC / IBC.

It is the Investigator's or designee's responsibility to obtain written permission to use protected health information from each subject. If a subject withdraws permission to use protected health information, it is the Investigator's responsibility to obtain the withdrawal request in writing from the subject and to ensure that no further data will be collected from the subject or used or disclosed except as necessary to protect the integrity of the study. Any data collected on the subject before withdrawal will be used by Sponsor and / or its designees in the analysis of study results in order to protect the integrity of the study. During the review of source documents by the monitors or auditors, the confidentiality of the subject will be respected in accordance with applicable professional standards and regulations.

11.4 Investigator's Report to the IEC / IBC

The Investigator is responsible for providing written summaries of the progress and status of the study at intervals not exceeding 1 year or otherwise specified by the IEC / IBC.

Upon completion of the study, the Investigator, where applicable, should submit to the IEC / IBC the summary of the study outcome.

11.5 Records Retention

The Investigator is responsible for retaining documents as required by local law and applicable regulations, as well as ICH standards. Essential documents should be retained until [REDACTED] [REDACTED] after the last approval of a marketing application in an ICH region and until there are no pending or contemplated marketing applications in an ICH region; or until [REDACTED] have elapsed since the formal discontinuation of clinical development of the investigational medicinal product. These documents should be retained for a longer period if required by the applicable regulatory requirements or by an agreement with the Sponsor. It is the responsibility of the Sponsor to inform the Investigator or institution as to when these documents no longer need to be retained.

11.6 Financial Disclosure

[REDACTED] For this study, each principal Investigator and sub-Investigator (as designated on the Form FDA1572) will provide a personally signed Financial Disclosure Form in accordance with 21 CFR Part 54. Each Investigator will notify the Sponsor or its authorized representative of any relevant changes in financial disclosure information during the conduct of the study and for 1 year after the study has been completed.

11.7 Liability and Insurance

In the event of a side effect or injury, appropriate medical care as determined by the treating physician/designee will be provided. The ICF will include a description of treatment in the event of a protocol-related injury and handling of the costs associated therewith, incorporating country-specific national regulations and / or local laws. [REDACTED]

[REDACTED]

12.0 STUDY MANAGEMENT

12.1 Monitoring of the Study

All aspects of the study will be monitored by the Sponsor or designee for compliance with applicable government regulation with respect to GCP and standard operating procedures.

Investigators and institutions involved in the study will permit study-related monitoring, audits, IEC review, and regulatory agency inspections, including by providing direct access to all study records.

In the event of an audit, the Investigator agrees to allow the Sponsor, representatives of the Sponsor, or applicable regulatory agencies an access to all study records. The Investigator should promptly notify the Sponsor or designee of any audits scheduled by any regulatory authorities and promptly forward copies of any audit reports to the Sponsor.

12.2 Data Quality Assurance

The Sponsor shall implement and maintain quality control and quality assurance procedures to ensure that the study is conducted, and that data are generated, documented, and reported in compliance with the protocol, GCP, and applicable regulatory requirements. This study shall be conducted in accordance with the provisions of the Declaration of Helsinki (October 2008) and all revisions thereof, and in accordance with the Food and Drug Administration (FDA) regulations (21 CFR Parts 11, 50, 54, 56, and 312, Subpart D—Responsibilities of Sponsors and Investigators) and with the ICH guidelines on GCP (ICH E6).

12.3 Data Management

The Investigator will prepare and maintain adequate and accurate source documents designed to record all observations and other pertinent data for each subject treated with the study drug.

The Investigator or other study personnel will enter information from the source documents onto case report forms (CRFs) that will be used to collect the clinical study data. A CRF must be completed for each enrolled subject with all required study data accurately recorded such that the information matches the data contained in medical records (e.g., physicians' notes, nurses' notes, clinic charts, and other study-specific source documents).

Authorized study site personnel (i.e., listed on the Delegation of Authority log) will complete CRFs designed for this study according to the completion guidelines that will be provided. The Investigator will ensure that the CRFs are accurate, complete, legible, and completed within a reasonable period of time. At all times, the Investigator has final responsibility for the accuracy and authenticity of all clinical data.

Study staff will be appropriately trained in the use of CRFs.

The Investigator attests that the information contained in the CRFs is true by providing signature within the data capture system.

After database lock, the Investigator will receive a copy of the subject data (e.g., paper, CD, or other appropriate media) for archiving at the study site.

13.0 STUDY COMPLETION

The study is expected to be completed at the timepoint when all subjects have completed or exited the protocol for any reason, or the protocol is terminated at the Sponsor's discretion, whichever occurs first.

15.0 APPENDICES

15.1 Appendix 1 Schedule of Assessments

Assessment ^a	Post-Treatment Assessment Timepoints			
	Screening ^b	Year 1 ^b [REDACTED]	Year 2 [REDACTED]	Year 3 (EOS) ^c [REDACTED]
ICF	X			
Inclusion/ Exclusion Criteria	X			
Review and record exposure to other investigational therapies	X	X	X	X
Record AEs of interest/related SAEs	X	X	X	X
Record conmeds ^d	X	X	X	X

Abbreviations: AE=adverse event; conmed=Concomitant medication; EOS=End-of-Study visit; ICF=Informed Consent Form; SAE=serious adverse event; [X]=optional.

- a Assessments may be conducted in the clinic or with a phone call by site personnel.
- b The Screening Assessment should be completed on the same day as the End-of-Study Visit in the prior ADVM-043 treatment study.
- c End-of-Study (EOS) Assessment is scheduled at 3 years post-treatment [REDACTED], or within [REDACTED] after subject withdrawal.
- d Only concomitant medications for A1AT deficiency (i.e., augmentation therapy), known mutagenic medications / agents, and medications to treat AEs of interest and SAEs related to ADVM-043 should be recorded.

15.2 Appendix 2 Mutagenic Medications / Agents

Classes of mutagenic medications / agents include, but are not limited to:

- alkylating agents (e.g., cyclophosphamide)
- anthracyclines (e.g., doxorubicin)
- platinum-based agents (e.g., carboplatin)
- retinoids (e.g., tretinoin)
- vinca alkaloids (e.g., vincristine)
- topoisomerase inhibitors (e.g., etoposide)
- antimetabolites / nucleotide analogues (e.g., methotrexate)
- aromatic hydrocarbons (e.g., benzene)
- toxic heavy metals and metalloids (e.g., arsenic)

2.1 Background

A clinical research subject who has been exposed to an investigational gene therapy may be at risk for delayed adverse events because of the vector that delivers the transgene or because of persistent biological activity of the investigational medicinal product. Some adverse events could be delayed by months or years. Therefore, to mitigate those risks, and per the United States Food and Drug Administration recommendations for the long-term follow-up observation of subjects who received gene therapy products, Study ADVM-043-03 is to be conducted in subjects previously treated with ADVM-043 and will follow them for a total of 3 years post treatment.

3 Study Objectives

3.1 Primary Objective

Assessment of the long-term safety of ADVM-043

3.2 Secondary Objectives

Not Applicable

4 Study Design

4.1 Overview

Study ADVM-043-03 is a post-treatment long-term follow-up study intended to collect safety data in subjects with A1AT deficiency who received ADVM-043 in a prior treatment study.

No investigational agent will be administered in Study ADVM-043-03.

The study population will comprise of subjects with A1AT deficiency who were previously treated with ADVM-043 in any clinical study.

4.2 Sample Size Justification

Not Applicable.

4.3 Randomization and Blinding

Not Applicable.

4.4 Inclusion/Exclusion Criteria

Inclusion Criteria:

1. *The subject has A1AT deficiency and has previously received ADVM-043 gene therapy.*

Exclusion Criteria:

1. *The subject is unwilling or unable to participate in all required study evaluations*

2. *The subject is participating in another investigational treatment protocol*
3. *The subject is unable to understand the purpose and risks of the study or cannot provide a signed and dated informed consent form (ICF)*

4.5 Treatment Allocation

Not Applicable.

5 Assessment Schedule

Subjects will be assessed for up to 3 years post-treatment with ADVM-043. The duration of this long-term follow-up period is 2 years.

Assessment ^a	Post-Treatment Assessment Timepoints			
	Screening ^b	Year 1	Year 2	Year 3 (EOS) ^c
ICF	X			
Inclusion/ Exclusion Criteria	X			
Review and record exposure to other investigational therapies	X	X	X	X
Record AEs of interest/related SAEs	X	X	X	X
Record conmeds ^d	X	X	X	X

Abbreviations: AE = adverse event; conmed = Concomitant medication; EOS = End-of-Study visit; ICF = Informed Consent Form; SAE = serious adverse event; [X] = optional.

^a Assessments may be conducted in the clinic or with a phone call by site personnel.

^b The Screening Assessment should be completed on the same day as the End-of-Study Visit in the prior ADVM-043 treatment study.

^c End-of-Study (EOS) Assessment is scheduled at 3 years post-treatment [REDACTED]; or within [REDACTED] after subject withdrawal.

^d Only concomitant medications for A1AT deficiency (i.e., augmentation therapy), known mutagenic medications / agents, and medications to treat AEs of interest and SAEs related to ADVM-043 should be recorded.

6 Interim Analysis

No interim analysis planned for this study.

6.1 Unblinding and Dissemination of Results

Not applicable.

7 Efficacy and Safety Endpoints

7.1 Primary Endpoint

1. *Type, frequency, severity, duration, and relationship to ADVM-043 of adverse events (AEs) of interest and serious adverse events (SAEs) related to ADVM-043.*

7.2 Secondary Endpoints

Not applicable

8 Statistical Methods

All analyses will be done using SAS (version 9.4, [REDACTED]).

Safety endpoints will be analyzed in a descriptive manner. Continuous data will be reported using the following descriptive statistics:

1. Number of observations (n)
2. Mean and Standard deviation (SD)
3. Median
4. Minimum (min) and Maximum (max)

Minimum and maximum values will be reported in the units of collection with 3 decimals being maximum value; the mean will be presented with 1 decimal place more and the standard deviation 2 decimal places more than the units of collection. Categorical data will be presented using frequency (n = number of subjects; m = number of events) and percentage (%).

Listings will be provided for all data recorded in eCRF to study subject profiles. All listings will be sorted by cohort, subject ID, and date (if applicable). Unscheduled visit data will only be listed and not included in summaries.

8.1 Handling Missing/Incomplete Data

Missing data will not be imputed.

8.2 Handling Outliers

Not applicable

8.3 Multiplicity Adjustment

Since the study is descriptive in nature, no multiplicity adjustment is required.

9 Analysis Populations

The membership of the analysis populations will be reviewed and finalized during the database lock.

Enrolled set will consist of all subjects who were previously treated with ADVM-043 in any clinical study.

The Full Analysis Set (FAS) consists of all subjects with A1AT deficiency who were previously treated with ADVM-043 in any clinical study and met all the eligibility criteria.

10 Analysis Variables

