4.3 Subject Withdrawal

A subject may withdraw from the study at any time and for any reason without prejudice to their future medical care by the Investigator or at the clinical study site.

Withdrawal from the study will occur under the following circumstances:

- Death
- Withdrawal of consent
- Lost to follow-up
- Study termination by Sponsor

If a subject is lost to follow-up, a minimum of two attempts should be made by the study site personnel to contact the subject. Appropriate contact includes 2 documented phone calls followed by a registered letter before a subject may be listed as lost to follow-up. The measures taken for follow-up and reason for premature study discontinuation should be documented in source documents and CRF.

When a subject withdraws from the study, the reason(s) for withdrawal are to be recorded on the CRF. Whenever possible, all subjects who withdraw from the study are to be encouraged to undergo the End-of-Study assessments at the time of withdrawal.

Sites should obtain follow-up data on any subject who withdraws from the study and has ongoing AEs of interest or SAEs related to ADVM-043. In every case, efforts must be made to undertake protocol-specified safety follow-up procedures.

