10.4 Protocol Deviations

A significant deviation is defined as a protocol deviation that affects primary assessments, the safety of a subject or the scientific value of the trial ([REDACTED] [REDACTED]). Significant deviations can include non-adherence to entry criteria; enrollment of the subject without prior Sponsor approval; or non-adherence to FDA regulations or ICH GCP guidelines. Protocol deviations will be reviewed prior to database lock to determine if significant, and all significant deviations will be flagged by the Clinical Trial Manager (CTM) and the Medical Monitoring (MM) team.

Any difference in the deviations classification will be discussed and finalized before the database lock. The protocol deviation summaries will be presented accordingly.

Deviation codes:

Deviations will be coded by the Clinical Trial Manager (CTM) and the Medical Monitoring (MM) team as below.

- Inclusion
- Exclusion
- Assessment – safety
- Visit window
- Informed consent
- Other

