11.7 Safety Analyses

The long-term safety of ADVM-043 is to be assessed by determining the type, frequency and percentages, severity, duration, and relationship to ADVM-043 of adverse events (AEs) of interest and serious adverse events (SAEs) related to ADVM-043. All safety data will be listed and summarized by cohort using the FAS population.

Only AEs of interest will be summarized.

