11.7.1 Adverse Events

All Adverse events will be coded using the Medical Dictionary for Regulatory Activities (MedDRA) version 21.0 or Higher. All summaries will be based on FAS population.

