11.7.1.3 Summary of Adverse Events by Severity

Number and percentage of subjects in each system organ class, preferred term, and intensity (Grade 1-5) will be summarized by severity for adverse events of interest and cohort. System organ class and preferred term will be displayed by descending order of frequency in “Total”.

12 Changes to Planned Analyses

No changes from the analysis defined in protocol.

13 Index of Tables, Listings and Graphs

Refer [REDACTED] for the list of Tables, Listings and Graphs.

14 References

Provide list of references used to create this document.

- ICH. ICH Harmonized Tripartite Guideline: Statistical Principles for Clinical Trials E9. 1998.
- ASA. Ethical Guidelines for Statistical Practice. Prepared by the Committee on Professional Ethics. 1999.
- ICH. ICH Harmonized Tripartite Guideline: Structure and Content of Clinical Study Reports E3. 1995.

15 Appendices

Not Applicable

16 Change Log

Version	Authored by	Change Date	Change Details	Reviewed by	Review Date
1.0	[REDACTED]	[REDACTED]	First Draft	[REDACTED]	[REDACTED]

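### SAP section 9 limits the set behind every adverse event table to subjects who satisfied all entry criteria, so a subject followed despite an entry violation would be counted in none of those tables

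*SAP*

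**What the plan says.** SAP section 9 defines two sets. The first is "Enrolled set will consist of all subjects who were previously treated with ADVM-043 in any clinical study". The second, the FAS, adds a condition: subjects "previously treated with ADVM-043 in any clinical study and met all the eligibility criteria". There is no safety set.

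Section 11.7 then states: "All safety data will be listed and summarized by cohort using the FAS population". Section 11.7.1 repeats it for adverse events: "All summaries will be based on FAS population". Adverse events of interest and related serious adverse events are the sole endpoint (SAP 7.1; 7.2 has no secondary endpoints).

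The plan foresees entry violations. SAP 10.4 says: "Significant deviations can include non-adherence to entry criteria", and it provides deviation codes for inclusion and exclusion criteria.

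On scope, protocol 8.0 says: "Descriptive and exploratory analyses are to be performed on all data to gain insight into the safety of ADVM-043". The same paragraph then refers the reader to the SAP. SAP section 12 says: "No changes from the analysis defined in protocol".

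**The concern.** Exposure to ADVM-043 took place in the earlier study, and nothing is administered in this one. A deviation from the entry criteria of the follow-up study therefore has no bearing on whether the subject was exposed or whether a malignancy or neurologic event occurred. An eligibility filter can serve a purpose in an efficacy comparison. In a descriptive safety study it can only remove observations.

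What is at stake is visibility. The tables are split into three dose cohorts and the events of interest are expected to be rare, so one dropped subject can decide whether a cohort shows any event at all. SAP 10.1 has the population flags set from the section 9 definitions before lock, so a programmer following the literal text would apply the filter.

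**Working it through.** The documents give no sample size (SAP 4.2 marks it not applicable), no cohort sizes and no event counts. There is no planned figure to reproduce. The check is a trace of populations, followed by an illustration on assumed cohort sizes.

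**1. Which set each output uses**

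| Output | Set |
|---|---|
| Overall adverse events (SAP 11.7.1.1) | FAS, stated |
| By organ class and preferred term, including related, serious and related serious (11.7.1.2) | FAS, stated |
| By severity (11.7.1.3) | none named, so the 11.7.1 rule gives FAS |
| Safety listings | FAS under 11.7; all eCRF data under section 8 |
| Subjects not meeting entry criteria (11.1) | Enrolled set |
| Significant deviations (11.3) | FAS |

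No adverse event table uses the Enrolled set. The 11.3 table has its own inconsistency: entry-criteria violations can be significant deviations, yet the subjects who have them cannot be in its FAS denominator.

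**2. Whether an entry violator can remain in follow-up**

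Protocol 4.3 opens its list with "Withdrawal from the study will occur under the following circumstances" and names death, withdrawn consent, loss to follow-up and termination by the sponsor. Ineligibility is not on it. Protocol 11.2 makes withdrawal after a significant deviation possible, not automatic. SAP 11.1 does list a major deviation among the reasons for not completing, but events seen before such an exit would also drop out of the tables.

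Of the four entry criteria, most leave little room. Prior treatment is required for either set. A subject without valid consent should have no assessments (protocol 5.0). A subject unable to take part would yield few data. Exclusion 2 is the realistic route.

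**3. The Year 1 re-check**

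Protocol 5.1 has eligibility reviewed at Screening and confirmed again before enrollment at Year 1. Appendix 1 records events from Screening, and SAP 10.6 defines a Screening to Year 1 period. A subject who fails the re-check may therefore already have events on record. The SAP does not say how that subject is classed, so this route is possible rather than certain. It may also be short: 3 years after treatment less a 2-year follow-up period puts entry at about 1 year for those who complete the earlier study. The window is longer for those who left it early, whom protocol 5.1 still screens.

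**4. Illustration (cohort size n is assumed)**

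With one event in the cohort and one subject excluded:

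- all followed subjects: 1/n
- FAS, if the excluded subject had the event: 0/(n − 1)
- FAS, if another subject had the event: 1/(n − 1)

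| n | All followed | FAS, event excluded | FAS, event kept |
|---|---|---|---|
| 3 | 1/3 = 33.3% | 0/2 = 0% | 1/2 = 50.0% |
| 6 | 1/6 = 16.7% | 0/5 = 0% | 1/5 = 20.0% |
| 10 | 1/10 = 10.0% | 0/9 = 0% | 1/9 = 11.1% |
| 20 | 1/20 = 5.0% | 0/19 = 0% | 1/19 = 5.3% |

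Exact 95% intervals overlap widely. At n = 6 they are 0.4% to 64.1% for 1/6 and 0% to 52.2% for 0/5, where the upper limit is 1 − 0.025^(1/5) = 0.522. What is lost is the case itself rather than precision. With no excluded subject, every row is unchanged.

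**The case against.** The best defence is that the clause was meant only to remove screen failures. Eligibility is checked twice before enrollment, and SAP 11.1 counts enrolled subjects, screen failures and FAS, then tabulates those not meeting entry criteria separately on the enrolled denominator. On that reading the Enrolled set is the wider group and the FAS is those who passed. This is plausible, but section 9 does not say so, and its wording also removes a subject who was enrolled in error.

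The affected group is also small, possibly empty. A new investigational therapy started after entry is recorded at each assessment (protocol 5.2). A reader might infer that it removes the subject from the FAS, but the criterion applies at entry, so it does not. This limits the size of the problem and stands.

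Safeguards exist too. Section 8 promises listings of all eCRF data, 11.3 lists significant deviations with their impact on the analysis, 11.7.1.2 lists deaths due to adverse events separately, and set membership is reviewed at lock. A reader might infer that a violator's events would vanish from the report; the documents do not support that. These provisions still put no event back into a table, and 11.7 ties safety listings to the FAS.

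Finally, a reader might infer that the SAP breaches protocol 8.0 and that section 12 is therefore wrong. That goes too far. Protocol 8.0 names no analysis population and leaves the detail to the SAP. Its reference to all data is in tension with the restriction and supports the point, but does not establish a breach.

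**Conclusion.** The point holds in conditional form. Read literally, SAP sections 9, 11.7 and 11.7.1 keep a subject followed despite an entry violation out of every adverse event table, and may do the same to a subject who fails the Year 1 re-check. This rests on three conditions: that such a subject exists, that safety information on that subject is recorded in this study, and that the flag is programmed as written. If any of them fails, the tables do not change.

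If all hold, one exclusion can turn a cohort's only event into none: from 33.3% to 0% at an assumed n of 3, and from 5.0% to 0% at an assumed n of 20. No test or decision rule is affected, since the study is descriptive. The text should be corrected because safety is the only endpoint and the correction is cheap. It is not evidence that the plan set out to remove safety data.

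**What to change.** - Define a Safety Set: all subjects previously treated with ADVM-043 who consented to ADVM-043-03 and have any safety information recorded in it, regardless of eligibility deviations or the result of the Year 1 re-check. Basing it on enrolled subjects would not be enough, because protocol 5.1 places enrollment at the Year 1 re-check and earlier events could still be lost.
- Use this set for all section 11.7 summaries and listings, which also brings the listings closer to section 8, and as the section 11.3 denominator. Flag entry violators in the output.
- Keep the FAS at most as a sensitivity set. If its eligibility clause was meant only to remove screen failures, say so.
- Reword the Enrolled set so that it refers to this study; at present it covers everyone ever treated.
- State the denominator for the section 11.1 table of subjects not meeting entry criteria, for example all consented subjects, because rewording the Enrolled set would otherwise disturb it.

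The cost is one SAP revision and one population flag before database lock. No new data are collected.
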